6.2.3. Other Endpoints

Other endpoints include:

- Change over time in speech reception threshold scores in the Sophono Alpha 2 and Alpha 2 MPO
- Change over time in word recognition scores in the Sophono Alpha 2 and Alpha 2 MPO

This document is electronically controlled. Printed copies are considered uncontrolled.

Confidential

7. Study Design

This study is an ambispective, multi-center, single-blind, intra-subject controlled study to assess safety of the Sophono implant and effectiveness of the Sophono Alpha 2 MPO processor in subjects with single-sided deafness (SSD), CHL, and mixed HL. This study will enroll approximately 100 subjects (with unilateral or bilateral implants) at up to 15 investigational sites in the US. (Investigational sites may include separate Audiology Centers, if applicable).

The subject population includes any patient who currently has or has had the Sophono implant, including those patients who have been explanted.

The study will consist of a retrospective medical chart review to collect data on AEs for all subjects upon receiving informed consent. A prospective clinic visit for subjects still implanted with the Sophono implant will be conducted to evaluate the subject's implant site and conduct hearing tests, along with a QOL and satisfaction self-assessment.

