10.1. Schedule of Events

After proper administration and signing of the IC and Research Authorization Forms, all potential subjects will be assessed for study eligibility based on the Inclusion and Exclusion Criteria. Inclusion and Exclusions data as well as limited demographic information will be captured in the subject CRFs.

A ***retrospective review*** of the subject's medical chart will be performed to gather and report data on subject surgical history, reportable AEs from the time of implantation to time of chart review, previous QOL scores, and previous audiometric testing results for Alpha 2 and/or Alpha 2 MPO processors.

An ***in-office visit*** will be conducted with an ENT physician and Audiologist, ideally on the same day, where the following assessments will take place:

ENT Visit:

The ENT visit will consist of an examination of the ear and implant site for skin complications (according to the *Holger Skin Evaluation Index* in Table 2) or other potential AEs (see Section 12 for reportable AEs). The ENT Visit CRF will detail findings (such as erythema, scar, etc.) as well as complications (skin loss, infection, etc.). Any such complications will be recorded on an AE form.

Sophono system satisfaction and QOL questions shall also be administered to allow the subjects' perceived benefits to be assessed. The QOL assessment will be done using the APHAB Version A.

Table 2. Holger Skin Evaluation Index

The skin directly over the implant site will be evaluated on the Holger Skin Evaluation Index.

Holger Skin Evaluation Index
0 = No irritation. Epithelium debris removed if present.
1 = Slight redness, local treatment.
2 = Red and slightly moist tissue. No granuloma formation noted. Local treatment. Extra controls.
3 = Status as in 1 and 2 but local revision became necessary.
4 = Removal of skin-penetrating implant necessary due to infection.
R = Removed implant for reasons not related to skin problems.

Audiology Visit:

All audiometric testing equipment should be calibrated and tested to American National Standards Institute (ANSI) standards, in good repair and functioning well.

All tests should be performed in the order presented in Table 3. Subject will be blinded to processor order.

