Information regarding any reportable AEs and outlined in Tables 4 & 5 below, in relation to the device or the procedure (as determined by the Investigator) that occur during the study will be recorded. This information will include, at a minimum, the date of the event, the seriousness of the event (prospective), the severity, actions taken, the outcome, and the relationship (if any) of the event to the device. Subject continuation in the study as prescribed in this protocol following an AE is anticipated, unless determined otherwise by the Investigator.

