12.2. Reporting of Adverse Events

Clinical information on AEs (as defined above), their presentation, date of event, management, relationship and outcome must be reported on a CRF and sent to Medtronic. Subjects with ongoing AEs at the time of the prospective visit may not exit the study until the AE has been resolved or is determined not able to be resolved. As this is a post-market study of a marketed device the sponsor and investigator will comply with regulations on event reporting according to the Medical Device Reporting System (MDR). The designated study personnel will have two opportunities to collect AE's for each subject:

At the retrospective data collection of Sophono implantation and post-implantation, any surgical procedure or device related AE will be recorded on the applicable CRF. This data collection may occur at any time after the subject consents to the study. No safety reporting to IRBs will be required for retrospective events.

At the follow-up visit, the designated study personnel will examine and query the subject on the experience of any AEs, and designated study personnel will record data on the applicable CRF. This data collection may occur at any time after the subject consents to the study. These prospective observed events will be reported to IRBs or other committees according to the rules and timeframe of the governing site or IRB.

No AEs will be collected after the subject exits the study.

13. Statistical Design and Methods

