13.3. Safety endpoint

Event rates, weighted for center, will be displayed together with their 95% confidence interval (95%CI); for each possible sub-group, analyses will be compared by means of a mixed Poisson model, with center included as random effect. In the presence of over dispersion, negative binomial regression will be used. Over dispersion will be assessed both with a goodness-of-fit test and a likelihood ratio test for $\alpha=0$. The incidence rate ratio (IRR) and 95%CI will be reported [IRR=rate group1 / rate group2]. The exposure time (days/months) will be computed from implantation to the date of the follow-up visit for each patient [(data end – data in)/30.4].

Specific events will be analyzed using survival analysis. The analysis will be supported by a Kaplan Meier curve indicating the number of patients at risk and comparison of curves will be done using the generalized Log-Rank Test where appropriate. The exposure time (months) will be computed from the date of the implantation to the date of the last available follow-up or date of event: [(data end – data in)/30.4].

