7.10.1 Primary endpoint

The primary safety endpoint is the proportion of AEs related to the Sophono implant or surgery, which will be assessed through retrospective surgical chart review and prospective ENT exam. The primary safety endpoint will be evaluated on FAS. The AEs used for this endpoint are according to Investigator's determination of the event's relatedness to the device or surgery.

Adverse Event rates will be displayed together with their 95% confidence interval (95%CI) overall, by site and by type of event.

A time to first Adverse Event will be performed using survival analysis. The analysis will be supported by a Kaplan Meier curve indicating the number of patients at risk and any possible comparison of curves between groups will be done using the Log-Rank Test where appropriate.

Table x - Primary safety endpoint – Sophono Implant related Adverse Events rates

Figure x - Kaplan Meier estimate of first Sophono Implant related Adverse Event occurrence

Table x - Kaplan Meier estimate of first Sophono Implant related Adverse Event occurrence

The primary effectiveness endpoint is the absolute difference (gain) in the free-field pure tone audiometry assessed by PTA unaided (AC) and aided by the Alpha 2 MPO processor. The primary effectiveness endpoint will be evaluated on PPS.

The difference between unaided and aided measurements will be analyzed by means of paired (samples) t-test or Wilcoxon signed rank sum test according to the normal or non-normal distribution.

Additional analysis will be performed on:

- the "within indication" subset will exclude from the analysis subjects whose Prospective AC & BC tests do not meet the device indications for use.

- The subsets defined by implanted ear diagnosis. For the subject affected by SSD, analyses will be performed for both the derived variables (both NR substitution methods).

Table x - Primary effectiveness endpoint - Difference in PTA between unaided (AC) and aided by the alpha 2 MPO Processor (Audiogram Results Gain)

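### The Kaplan-Meier analysis of time to first AE has no rule for AEs first seen at the single ENT visit with unknown onset; dating them to the visit would understate early risk and overstate the tail

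*SAP*

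**What the plan says.** SAP 7.10.1, under the primary safety endpoint: "A time to first Adverse Event will be performed using survival analysis". It lists a Kaplan-Meier figure and table, numbers at risk, and log-rank tests where groups are compared. The AEs are those "which will be assessed through retrospective surgical chart review and prospective ENT exam".

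The two sources differ in kind:

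- **Chart review** (Protocol 10.1) covers "reportable AEs from the time of implantation to time of chart review".
- **The ENT visit** happens once. Protocol section 7: "A prospective clinic visit for subjects still implanted with the Sophono implant will be conducted". Protocol 12.2: "At the follow-up visit, the designated study personnel will examine and query the subject on the experience of any AEs". The implant site is graded on the Holger index, and Table 5 makes grades 2 to 4, abnormal scarring, numbness and hair loss reportable.

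Protocol 9.3 requires at least 3 months since implantation and sets no upper limit, so the visit can fall at widely different times.

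On dating, Protocol 12.1 says "This information will include, at a minimum, the date of the event", and 12.2 repeats the requirement: "Clinical information on AEs (as defined above), their presentation, date of event, management, relationship and outcome must be reported on a CRF". Protocol 13.3 has survival time "computed from the date of the implantation to the date of the last available follow-up or date of event". SAP 7.6 instead derives time to first AE as the study evaluation date minus the date of the first AE. SAP 7.4 rules out imputation. Neither document covers a finding whose onset is unknown.

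**The concern.** A scar, numb patch or Holger grade 2 site seen for the first time at the visit may be known only to have begun at some point before it. The date field has to be filled, and with no rule the visit date is an obvious entry. For most attenders the visit is also the last available follow-up, so such an event would sit at the end of that subject's own observation time. Events placed this way follow the visit schedule rather than the onset of AEs.

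At stake is the shape of the Kaplan-Meier figure and table listed under the primary safety endpoint, and any log-rank comparison of groups whose visits fell at different times after implantation. The AE proportion itself is not at stake: whether a subject had an AE does not depend on how it is dated.

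**Working it through.** The plan gives no Kaplan-Meier figure to reproduce and no share of AEs first found at the visit. What follows is a range under stated assumptions.

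**Inputs**
- AE by the time of the visit: 14% of subjects, borrowed from the incidence in Protocol 13.1.
- Visit time: uniform over 3 to 60 months after implantation. The 3-month minimum is in Protocol 9.3; the upper end and the shape are assumptions.
- Onset: constant hazard h (assumption). Findings persist until the visit (assumption).
- q: share of AEs dated to the visit because onset is unknown. Not in the documents; varied from 0 to 100%.

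**Truth.** Setting the average of 1 − exp(−h·v) over v from 3 to 60 equal to 0.14 gives h = 0.00489 per month. The true cumulative incidence is F(t) = 1 − exp(−h·t): 5.7% at 12 months, 16.1% at 36, 20.9% at 48 and 24.3% at 57.

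**Mechanism.** At time t the risk set holds subjects without an AE (proportion 1 − F) and subjects with an AE not yet dated (q·F). The visit hazard is 1/(60 − t). The hazard that Kaplan-Meier estimates is therefore

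[q·h(1 − F)(1 − q)/q + q·F/(60 − t)] / (1 − F + q·F),

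which simplifies to [(1 − q)·h·(1 − F) + q·F/(60 − t)] / (1 − F + q·F).

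With q = 25%:
- At 12 months: (0.75 × 0.00489 × 0.943 + 0.25 × 0.057/48) / (0.943 + 0.014) = 0.39% per month, against a true 0.49%.
- At 57 months: (0.75 × 0.00489 × 0.757 + 0.25 × 0.243/3) / (0.757 + 0.061) = 2.8% per month, against 0.49%.

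So the curve starts too low and then climbs steeply as the last visits take place.

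**Simulation** (100 subjects, 3,000 runs; a repeat with 12,000 runs agreed to within about 0.3 points). Kaplan-Meier cumulative incidence on the Protocol 13.3 axis:

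| Share dated to visit | 12 months | 36 months | 48 months | 57 months |
|---|---|---|---|---|
| Truth | 5.7% | 16.1% | 20.9% | 24.3% |
| 0% | 5.7% | 16.2% | 21.0% | 24.4% |
| 25% | 4.4% | 14.2% | 20.6% | 30.1% |
| 50% | 3.1% | 12.2% | 20.3% | 34.9% |
| 100% | 0.7% | 8.3% | 19.4% | 41.4% |

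With onset clustered early (Weibull shape 0.5), the truth at 12, 36 and 57 months is 9.3%, 15.6% and 19.2%. A 25% share gives 7.3%, 14.1% and 25.4%; a 50% share gives 5.2%, 12.8% and 30.5%.

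**SAP 7.6 taken literally.** Study evaluation date minus AE date is zero for an AE dated to the visit. The SAP gives no formula for subjects without an AE; they are taken here as censored at implantation-to-visit time. With q = 100% every event is at time zero and the curve is flat at 14%. With q = 50% it reads 7.6% at 3 months against a true 1.5%, and 20.0% at 57 months against 24.3%. The distortion is reversed.

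**Dropping the undated findings.** If they are removed as events and the subjects censored at the visit, a 25% share gives 18% at 57 months against 24%.

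**The case against.** The strongest reply is that the plan nowhere says to use the visit date. Both Protocol 12.1 and 12.2 require the date of the event, Protocol 13.3 runs time to the event rather than to its detection, and staff must question the subject as well as examine. Many Table 5 criteria involve treatment or a course of symptoms that the chart or the subject could date. This stands: an AE with a documented or credibly reported onset is handled correctly, and if all are, there is no bias. What remains is the AE whose onset nobody can give, for which there is no rule.

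A reader might go further and infer that all exam-found AEs enter on the day of censoring, that the data are simply current-status data, and that the curve would show rising risk where true risk is flat. With a constant 10% prevalence at the exam, the closed form 1 − G^0.10 (G being the share not yet visited) gives 6.7%, 20.6% and 25.9% when half, 90% and 95% of visits are past. The documents do not support that reading. Chart review supplies dated history, so the closed form, which treats every AE as found only at the exam, is the extreme case. Moreover, 10% is a point prevalence, while the curve estimates cumulative first-AE incidence. The two agree only if every finding is present from the start and never resolves. If episodes last 24 months on average at a steady 10% prevalence, the onset rate is (0.10/0.90)/24 = 0.00463 per month and the true incidence at 60 months is 1 − 0.9·exp(−0.00463 × 60) = 32%, so late overstatement need not follow.

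Three further points stand. Event and censoring day need not coincide, since Protocol 12.2 keeps subjects with ongoing AEs in the study and explanted subjects have no visit; but later follow-up does not move a first event already dated. The tail is thin: only (60 − 57)/(60 − 3) = 5% of visits fall after 57 months here, and the planned numbers at risk would show it. Finally, the curve supports the AE rate and carries no decision threshold.

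**Conclusion.** The gap is real and modest. An ordinary Kaplan-Meier curve is planned on two AE sources, one of which can yield events of unknown onset, and nothing says how those enter. If they take the visit date on the Protocol 13.3 axis, early and mid-curve risk is understated and the tail overstated: for a 25% share, by about 1.3 points at 12 months (4.4% against 5.7%) and 6 points in the other direction at 57 months (30% against 24%), with little error at 48 months. This rests on the assumed visit distribution, constant hazard, 14% incidence and persistent findings; the share itself is unknown and could be nil. Under SAP 7.6 as written the direction reverses, because a visit-dated AE falls at time zero. That formula conflicts with Protocol 13.3 and has to be corrected in any case, but correcting it alone leaves the dating gap open. The crude AE proportion is untouched, so this is an inexpensive improvement to a supportive analysis and does not threaten the primary safety estimate.

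**What to change.** In SAP 7.6 and 7.10.1:

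1. Define time to first AE as first AE date minus procedure date, with subjects without an AE censored at explant or last follow-up.
2. Record for each AE whether the date entered is a known onset or only the date of detection. The date alone cannot show this, so it needs one indicator.
3. For exam-found AEs of unknown onset, add an interval-censored (Turnbull) estimate. The interval runs from the last documented AE-free contact, or from implantation if there is none, to the visit. Present it beside the Kaplan-Meier curve, at least as a sensitivity analysis.
4. Report the point prevalence of these findings among examined subjects. Do not simply drop them from the curve, since that biases it low.

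The cost is SAP wording, one onset-known indicator and a little more analysis; no visit is added. Last AE-free contact is not among the listed chart items, so where it is not abstracted the interval starts at implantation and is wide. With few events the interval-censored estimate will be imprecise, which reflects what the data can show.

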7.10.2 Secondary endpoints

For secondary endpoints the PPS population will be used for analysis.

7.10.3 Secondary endpoint#1

The secondary objective#1 will be evaluated as the difference in the free-field pure tone audiometry assessed by PTA aided by Alpha 2 processor compared to the PTA aided by Alpha 2 MPO processor. The difference between Alpha 2 and Alpha 2 MPO measurements will be analyzed by means of paired (samples) t-test or Wilcoxon signed rank sum test according to the normal or non-normal distribution.

Table x - Difference in PTA by device (Audiogram Results Gain)

Figure x - PTA by device type

7.10.4 Secondary endpoint#2

The secondary objective#2 will be evaluated as the change over time in the free-field pure tone audiometry assessed by pure tone average (PTA) aided in the Sophono Alpha 2 and Alpha 2 MPO.

The change over time (Retrospective vs Prospective data) of the PTA measurements will be analyzed by means of paired (samples) t-test or Wilcoxon signed rank sum test according to the normal or non-normal distribution and reported for each processor (Alpha 2 and Alpha 2 MPO).

The plots for the mean change over time will be reported.

Table x - Change over time of PTA Aided by Alpha2 processor by time and Aided by Alpha2 MPO processor by time

Figure x - Change over time of PTA Aided by Alpha2 processor by time

Figure x - Change over time of PTA Aided by Alpha2 MPO processor by time

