Study Procedures and Assessments	
After proper administration and signing of the Informed Consent (IC) and Research Authorization Forms, all potential subjects will be assessed for study eligibility based on the Inclusion and Exclusion Criteria.
 
Retrospective data collection from medical charts for safety and baseline data will be collected by the site.
 
Prospective Data Collection (visit):
 
• ENT visit
• Examination of implanted ear• Satisfaction Questions• QOL questions: Abbreviated Profile of Hearing Aid Benefit (APHAB)TM Version A• Audiologist Visit: Optimization of device programming for all aided tests should be completed.
• Hearing in Noise Test: BKB-SIN• Speech and Language Tests: Word Recognition Score, Speech Reception Threshold• Audiograms:
• Baseline AC Thresholds at octave intervals at 250, 500, 1000, 2000, 3000, 4000 and 8000 Hz• Test Baseline BC and Aided Thresholds at 500, 1000, 2000, 3000 and 4000 Hz• Subjects are blinded to processor types for all tests

This document is electronically controlled. Printed copies are considered uncontrolled.

Confidential

	
Audiogram Test Design
 
  
 Tests	Subject has Alpha 1, Alpha 2, or Alpha 2 MPO Processor*	
   
 Test 1	No processor	
 
 Test 2	Alpha 2	
 
 Test 3	Alpha 2 MPO	
  
 
*Alpha 2 and Alpha 2 MPO processors will be provided to each site for use in the study. Thus, regardless of the processor the subject wears daily, both Alpha2 and Alpha 2 MPO can be tested on each subject.
	Tests	Subject has Alpha 1, Alpha 2, or Alpha 2 MPO Processor*	Test 1	No processor	Test 2	Alpha 2	Test 3	Alpha 2 MPO
Tests	Subject has Alpha 1, Alpha 2, or Alpha 2 MPO Processor*								
Test 1	No processor								
Test 2	Alpha 2								
Test 3	Alpha 2 MPO								

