8.1.3. Sound Processors

The Sophono Processor is an audio processor that converts sound into mechanical vibrations. Sound enters the audio processor through the microphones, which then goes through [REDACTED]

[REDACTED] The vibrations are carried through the patient's skin and skull to the cochlea where they are perceived as sound. The Sophono Sound Processors have a simple user interface with a combined on/off and volume switch wheel, and a push button switch that allows the user to swap between four programmable settings configured by the clinician during the fitting session.

Table 1. Sophono Sound Processors

Sophono Sound Processor	Product Number
Alpha 1	S0001-XX
Alpha 2	S0415-XX
Alpha 2 MPO	S0415-XX
Alpha 2 MPO Low Profile	S0415-XX

This document is electronically controlled. Printed copies are considered uncontrolled.

Confidential

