8.8. Product Storage

Each participating site will receive one Alpha 2 and one Alpha 2 MPO sound processor to use as a comparator in the study. These processors will be stored in a secure location at the clinical site with access restricted to designated study personnel only. Storage requirements should be in accordance with the Instructions for Use provided with the processors, sites' operating policies, and applicable federal and geographic regulations.

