13.4. Effectiveness endpoint

The change between unaided and aided measurements will be analyzed by means of paired (samples) t-test or Wilcoxon signed rank sum test according to the normal or non-normal distribution or McNemar test for categorical variables where appropriate. Categorical variable comparisons will be performed using a Chi-square test or a Cochran-Mantel-Haenszel test for trend for ordinal variables with 3 or more categories. The mean change will be displayed together with their 95% confidence interval (95%CI).

Analysis of secondary endpoints based on comparisons between groups on continuous measurements will be performed by Student's t-test or non-parametric test (Mann–Whitney U test) for normal and non-normal distributions, respectively. Normality will be assessed by means of Shapiro-Wilks test and the p-value will be reported. Analysis of secondary endpoints based on the change over time (if more than 3 measurements) will be analyzed by means of GEE models or mixed models for continuous outcomes to account for repeated measures using patient as the subject. The dependent variable will be pre-log transformed depending on normal or non-normal distribution. The model will have the clinical outcomes as dependent variables and baseline values, visits and other covariates as explanatory variables. All assumptions for regression models will be assessed by viewing plots of the residual values. The plot for the mean change over time will be reported.

14. Ethics

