PTA (dB)	The PTA will be calculated as average of the derived audiogram Hz values. For the AC test all the available values at 250Hz, 500Hz, 1000Hz, 2000Hz, 3000Hz, 4000Hz and 8000Hz will be considered in the calculation. For the BC or Aided tests all the available values at 500Hz, 1000Hz, 2000Hz, 3000Hz and 4000Hz will be considered in the calculation. Missing or VT values will not be considered in the calculation.
Gain (dB) in the free-field pure tone audiology	Absolute difference between PTA values
Time to first AE (days)	Study Evaluation- First AE occurrence date ¹
Total time in hospital (days)	Discharge date – Admission date

¹ if more than one procedure or event, consider the date of the first one.

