7.10.6 Secondary endpoint#4

The secondary objective#2 will include the change over time in speech reception threshold and word recognition scores in the Sophono Alpha 2 and Alpha 2 MPO.

The change over time (Retrospective vs Prospective data) of the SRT (dB), WRS (%) and SNR Loss (%) measurements will be analyzed by means of paired (samples) t-test or Wilcoxon signed rank sum test according to the normal or non-normal distribution and reported for each processor (Alpha 2 and Alpha 2 MPO).

The plots for the mean change over time will be reported.

Table x – Change over time in speech reception threshold and word recognition scores aided by Alpha2 processor by time and by Alpha2 MPO processor by time

Figure x – Change over time of SRT (dB) aided by Alpha2 processor by time

Figure x – Change over time of WRS (%) aided by Alpha2 processor by time

Figure x – Change over time of SNR Loss (dB) aided by Alpha2 processor by time

Figure x – Change over time of SRT (dB) aided by Alpha2 MPO processor by time

Figure x – Change over time of WRS (%) aided by Alpha2 MPO processor by time

Figure x – Change over time of SNR Loss (dB) aided by Alpha2 MPO processor by time

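### The change-over-time tests compare chart results obtained under unspecified conditions with standardized study tests, so any systematic difference in conditions would be counted as change over time

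*SAP*

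**What the plan says.** SAP 7.10.4 defines the analysis: "The change over time (Retrospective vs Prospective data) of the PTA measurements will be analyzed by means of paired (samples) t-test", or a Wilcoxon signed rank test if the data are not normal, reported for each processor. SAP 7.10.6 repeats it for speech: "The change over time (Retrospective vs Prospective data) of the SRT (dB), WRS (%) and SNR Loss (%) measurements will be analyzed" in the same way.

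The two members of each pair come from different sources.

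- **Study test.** The Protocol synopsis (Study Procedures and Assessments) says: "Optimization of device programming for all aided tests should be completed". Protocol 10.1 has processors begin at 100% optimization and come down only when the subject cannot tolerate the feedback. It also specifies plugging of the good ear, masking and recorded speech. On the units, Protocol 8.8 says: "Each participating site will receive one Alpha 2 and one Alpha 2 MPO sound processor to use as a comparator in the study".
- **Chart test.** Protocol 10.1 asks only for "previous audiometric testing results for Alpha 2 and/or Alpha 2 MPO processors", and SAP 5.3 is no more specific. Neither gives a setting, unit, plugging or masking condition, time window, or rule for choosing among several chart audiograms.

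SAP 7.6 builds the aided PTA from what is present: "For the BC or Aided tests all the available values at 500Hz, 1000Hz, 2000Hz, 3000Hz and 4000Hz will be considered in the calculation". Protocol 13.4 foresees "GEE models or mixed models for continuous outcomes to account for repeated measures", with covariates, but only when there are more than 3 measurements, and device settings are not named among the covariates.

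**The concern.** Secondary objective 2 asks whether effectiveness is maintained over time. The only inferential analysis of it is a single mean difference between an uncontrolled measurement and a controlled one. In that difference, time and the switch from chart conditions to study conditions are completely aliased. If conditions differ systematically, the test can report an improvement or decline that did not occur, or cancel a real one. A larger sample makes a spurious result more likely.

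Elapsed time does not enter the analysis. Eligibility requires only 3 months or more with the implant (Protocol 9.3), and no interval between the two tests is defined, so a pair months apart and a pair years apart count equally.

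Two details add to the problem. Protocol 8.1.3 notes that the processor "allows the user to swap between four programmable settings configured by the clinician during the fitting session", so an earlier test on the same model need not have used the same program. And because PTA uses whichever frequencies are available, the two members of a pair may be averages over different frequencies.

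**Working it through.** **No stated figure to reproduce.** Neither document gives an effect size, SD, power or number of pairs for this endpoint. What follows is an illustration.

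**Inputs from the documents.** Two-sided 0.05 (SAP 7.2); no multiplicity adjustment (SAP 7.5); about 100 enrolled with 25% dropout (SAP 6), so at most about 100 × 0.75 = 75 pairs; SD of PTA 8.2 dB unaided and aided (Protocol 13.1).

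**Assumed inputs.** The number of subjects with a usable chart audiogram per processor is not given; 30 and 75 pairs are shown. The SD of a chart-to-study difference is not given either. If each measurement has SD 8.2 dB and the correlation is ρ, then SD of change = 8.2 × √(2(1 − ρ)). This is 11.6 dB at ρ = 0 and 8.2 dB at ρ = 0.5. A third value, 5 dB, is assumed (ρ about 0.81, from 1 − 25/(2 × 67.24)). The shift is assumed to be 2, 3 or 5 dB.

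**Formula.** With zero true change, the paired t statistic follows a noncentral t distribution with n − 1 degrees of freedom and noncentrality δ = shift × √n / SD. The chance of a significant result is P(|T| > t), where t is 2.045 for n = 30 and 1.993 for n = 75.

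For a 3 dB shift and 30 pairs, δ = 3 × 5.477 / SD. That is 3.29 at SD 5, 2.00 at SD 8.2 and 1.42 at SD 11.6.

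| Shift | SD 5, n=30 | SD 8.2, n=30 | SD 11.6, n=30 | SD 8.2, n=75 | SD 11.6, n=75 |
|---|---|---|---|---|---|
| 0 dB | 5% | 5% | 5% | 5% | 5% |
| 2 dB | 56% | 25% | 15% | 55% | 31% |
| 3 dB | 89% | 49% | 28% | 88% | 60% |
| 5 dB | >99% | 90% | 63% | >99% | 96% |

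**Masking.** Take 30 pairs, SD 7 dB and intervals uniform from 0.25 to 4 years (mean 2.125), all assumed. A true decline of 2 dB per year averages 2 × 2.125 = 4.25 dB. An opposite shift in conditions of 4.25 dB leaves the paired test significant in about 5% of trials.

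**What a regression on elapsed time can do.** Under the same assumptions the intervals have SD 3.75/√12 = 1.083 years, so the standard error of the slope is about 7 / (1.083 × √29) = 1.20 dB per year. By simulation:

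- Constant 3 dB shift, no time effect: the slope test rejects in about 5% of trials, the paired test in about 62%.
- True change of 2 dB per year, no shift: slope power is about 35%, paired power about 87%.
- No true time effect, but a shift that grows by 1 or 2 dB per year of interval: the slope test rejects in about 13% or 36% of trials.

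**Is there a safeguard elsewhere?** The model in Protocol 13.4 is conditional on more than 3 measurements, does not name settings, and is not carried into SAP 7.10.4. SAP 7.13 says only that analyses may differ from the protocol because of data availability. SAP 7.6 sets no common-frequency rule. None of these separates a change in conditions from a change over time.

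**The case against.** **The documents do not show that a shift exists.** A reader might infer that the chart audiograms were taken at everyday settings, and hence that the plan will report a spurious improvement. The documents do not say so. They are silent on chart settings, and some of those tests may have followed a fitting or optimization session. Nor is the study test always at maximum, since it may be lowered for feedback. Existence, size and direction are all unknown. This stands, and it limits the point to 'would be counted if present'. It does not rescue the analysis, because nothing in the plan could detect or remove a difference.

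**The rejection rates restate the assumed shift.** True. They are power calculations for assumed inputs and vary widely with the SD. They show sensitivity, not a predicted error rate.

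**A slope test is not a clean replacement.** Also true. A reader might take its 5% rejection rate as proof that it solves the problem, but that follows from assuming a shift unrelated to elapsed time. It fails if, say, older fittings were less well optimized, and the power loss is large. The intercept equals the chart-to-study shift only if change is linear from time zero; early acclimatization would be absorbed into it. The slope can be supportive only.

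**The contrast is inherent in an ambispective design and the endpoint is secondary.** With one chart value and one study value, a per-processor paired comparison is a conventional summary, and neither primary endpoint is touched. This argues for relabelling the comparison, not for leaving it as a test of change over time.

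**Conclusion.** The concern holds in a limited form. The paired comparisons in SAP 7.10.4 and 7.10.6 cannot distinguish change over time from a change in test conditions, and they ignore elapsed time. A significant result would not support a conclusion on secondary objective 2, and a non-significant one would not show stability.

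The size is unknown from the documents. For an assumed 3 dB shift, 30 pairs and no true time effect, the chance of a significant result is about 28% to 89% over SDs of change from 11.6 down to 5 dB, against a nominal 5%. With no systematic shift, the paired test keeps its nominal level. The documents do not support the stronger claims that a settings effect is present, that it favours the study test, or that a false improvement will be reported. The primary endpoints and the sample size are unaffected.

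**What to change.** In SAP 7.10.4, and likewise in 7.10.6 for SRT, WRS and SNR loss:

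1. Report the paired mean change with its 95% CI for each processor, labelled 'chart versus study test', as descriptive and not as evidence of change over time.
2. For this comparison, compute both PTAs on the frequencies available at both tests.
3. Add a supportive regression of each subject's signed change (study minus chart) on years between tests. Report the slope with its CI, and state that it has low power and assumes any shift in conditions is unrelated to elapsed time.
4. Where the chart documents processor, settings and test conditions, add a sensitivity analysis limited to comparable pairs, and report how many pairs qualify.
5. State which chart result is used when there are several.

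The cost is SAP wording, one regression per outcome and processor, and extraction of the chart test date, frequencies and, where recorded, conditions. The documents do not show whether the case report form already captures these. No visit, procedure or sample size changes. The drawback is a weaker claim for secondary objective 2: a descriptive contrast and an imprecise slope in place of a p-value.
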